ii). Institute for Clinical and Evaluative Sciences (ICES) Data: A Unique Opportunity to Evaluate System-Level Impact – Meeting the Mandate of the Innovative Clinical Trial (ICT): Using data from ICES, which captures all physician and hospital-provided insured services in Ontario, we will compare population-based outcomes (hospitalizations, emergency department visits, suicide attempts and mortality) with two comparison groups: 1) all EPI program FEP patients who have not been part of the NAVIGATE trial; and 2) all FEP patients who are not attached to EPI programs. All EPI programs in Ontario report their service utilization data through the Ontario Common Assessment of Need (OCAN) dataset (OCAN is linked to ICES data). While accuracy of data within OCAN is variable, we have confirmed that we can accurately ascertain the initiation date of all EPI patients by sex within Ontario through ICES linkage. The ability to link NAVIGATE's primary clinical and implementation data with ICES data, and the capacity to identify all FEP patients in Ontario (whether treated in EPI programs or not) allows for a meaningful, valid, and highly generalizable comparison of outcomes. The use of propensity score methods will address confounding associated with observational studies, and mimics some of the characteristics of a randomized controlled trial⁵¹. Since outcome data across all comparison groups are routinely collected by ICES, this dramatically reduces the time and cost of a randomized controlled trial (RCT) (thus fulfilling the ICT mandate), because the study does not require costly, extensive follow-up.

ICES has developed a costing macro that we have used to study health care costs among individuals in Ontario with schizophrenia⁵². The costing macro ensures that we have the capacity to determine costs associated with NAVIGATE relative to EPI usual care and no EPI care, a key implementation outcome. Cost estimation adds to the feasibility and policy-relevance of scaling up.

3. Statement of Objectives and Hypotheses

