Although each EPI program has existing processes for providing the components of early psychosis care, these are not necessarily delivered in the systematic and intentional manner outlined through NAVIGATE. Building on a large body of practice change evidence supporting a ‘make it happen’ rather than ‘let it happen’ approach^{34,58}, we will guide each program site through a facilitated, staged, change process informed by the Active Implementation Framework and the Quality Implementation Framework^{34,59}. A regional PSSP facilitator will have primary responsibility for the implementation, working closely with the CAMH NAVIGATE experts, and EPI program staff lead at each site. The CAMH NAVIGATE experts and PSSP facilitator will bring expertise and momentum to the work. The PSSP facilitator, EPI program staff lead, and ECHO team will assist with site engagement, understanding and preparing the program context, and local problem-solving⁶⁰.

Although sites will vary somewhat in their pace of implementation, we expect that installation (see below) will occur across the first six months, that trialing and refining will occur during months 7-12, and that practice will become embedded after month 12. Thus, PSSP involvement and facilitation will be most intense during early and mid-implementation stages as sites plan, trial and refine, and will decrease as delivery practices stabilize and become routine. The facilitators will monitor program progress in a task log based on Meyers⁵⁹. Achievement of key implementation milestones will be reported and areas flagged where more support may be needed. Correspondingly, involvement of ECHO will increase over time to support NAVIGATE as part of routine practice and this will also be monitored. The stages of our implementation process include:

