Stage 1. Exploration (to assess site capacity and need, build engagement): This stage is key to successful practice change. As EPION members who are committed to this project, there is already considerable engagement among participating sites. Additionally, having participated in the prior sector surveys and fidelity reviews, NAVIGATE was identified as a strategy to improve upon current practice at each site. In this stage the CAMH NAVIGATE experts, PSSP facilitators, and ECHO team will meet with each site to explain NAVIGATE, learn about their current staffing and service delivery processes, and discuss how NAVIGATE could be integrated into their practice. Staff will complete a site readiness assessment survey and a program fidelity review will be conducted to learn more about site capacities and needs for NAVIGATE implementation.

Stage 2. Installation (to create structures/build capacity for implementation): Intensive staff training over several days will include a didactic component, role playing, and discussions with individual sites to best fit NAVIGATE with each site’s current processes. The training will initially require three days at the coordinating site (CAMH, Slight Centre), co-led by NAVIGATE trainers from the RAISE study, or equivalent training. Regular site visits from PSSP facilitators and CAMH Slight Centre content experts will occur to develop the local implementation plan working with each site lead to prepare staff. Preparation for practice change will include discussions of: role allocation among staff (i.e. IRT vs. SEE vs. family psychoeducation program); whether the program needs to partner with an external service to deliver some elements (particularly the smaller sites); any changes to current patient flow required to deliver NAVIGATE (the care path); how contact and progress note data will be collected and used in meetings to review progress in NAVIGATE delivery; and how to prepare for ECHO sessions (topics and cases). The ECHO team will also work with each site to ensure set-up and ongoing functioning of infrastructure for live video-conferencing.

Stage 3. Initial implementation (trialing and refining) and Evaluation of Implementation Quality: During this stage, each site will begin NAVIGATE delivery and use feedback from various sources, including ECHO

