iv) AFFORDABILITY System Outcome – Cost (i.e. Implementation Evaluation Outcome iv):

We will employ a costing algorithm developed in SAS®, and available at ICES⁷³, to estimate all direct patient-level health care costs incurred by the public third-party payer (Ontario Ministry of Health and Long-Term Care) across the three comparison groups. We will include costs of hospitalizations (both non-psychiatric and psychiatric); ED visits; physician services (i.e. primary care, psychiatry and other care) and diagnostics tests; outpatient prescription drugs for individuals covered under the provincial public drug insurance plan only (for individuals under 65 who receive social assistance and currently universally for individuals under age 25); home care; long-term care; and other care (this includes other ambulatory care, such as same-day surgery/procedures, cancer and dialysis clinic visits, and other hospital-based care, such as rehabilitation and complex continuing care). The costing methodology used in the algorithm will include a bottom-up/micro-costing approach to cost services at the individual level. This approach will make use of individual episodes of care or utilization in the health care system and attached prices (or costs or amounts paid) to each one. A top-down approach, which allocates corporate aggregate (i.e. institutional) costs to individual visits or cases/episodes of care, will be applied in cases where individual unit costs are not available (e.g. for institutional care settings). Assuming that all subjects will incur health care costs, we will use a generalized linear model with a gamma distribution and log link to model health care costs. Actual model parameters will be determined by the nature of the cost distributions.

Covariates: We will extract information on sociodemographic characteristics, including age, sex, neighborhood-level income quintile, and rurality of residence. Clinical covariates will include type of diagnosis (schizophrenia, schizoaffective disorder, etc.), source of index diagnosis (hospitalization, outpatient visit), and history of visits with alcohol- or substance-related diagnoses. We will also measure prior service use for mental disorders, including the number of prior visits for mental health reasons with the primary care physician, visits to psychiatrist, emergency department visits related to mental health and addiction conditions, and previous psychiatric hospitalizations.

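### The affordability test counts health-service use only, so the NAVIGATE versus usual-EPI cost difference leaves out the extra cost of implementing NAVIGATE

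*Combined protocol and SAP*

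**What the plan says.** Section 4, under the evaluation of implementation outcomes (Objective 1), covers three of the four funder metrics and refers the fourth, affordability, to the system-level section. The subsection headed iv) AFFORDABILITY is therefore the only place where it is measured.

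That subsection uses an ICES algorithm "to estimate all direct patient-level health care costs incurred by the public third-party payer". The components are listed: "We will include costs of hospitalizations (both non-psychiatric and psychiatric); ED visits; physician services", then diagnostic tests, publicly covered drugs, and "home care; long-term care; and other care (this includes other ambulatory care, such as same-day surgery/procedures, cancer and dialysis clinic visits", with some further hospital-based care. On the bottom-up method it says: "This approach will make use of individual episodes of care or utilization in the health care system". A top-down method, which assigns institutional costs to visits or episodes, "will be applied in cases where individual unit costs are not available (e.g. for institutional care settings").

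The use made of the result is wider. Section 2.1 says the team can "determine costs associated with NAVIGATE relative to EPI usual care and no EPI care, a key implementation outcome" and ties costing to scale-up. Section 3.1, objective 2, lists system costs. Section 3.2, hypothesis 2, predicts lower costs with NAVIGATE.

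Section 4 also describes what is done to install NAVIGATE. "A regional PSSP facilitator will have primary responsibility for the implementation". "The training will initially require three days at the coordinating site", with trainers from the RAISE study or equivalent. There are regular site visits, and ECHO involvement grows as PSSP involvement declines.

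**The concern.** Training, facilitation and coaching are the main things this study adds at NAVIGATE sites that usual EPI sites do not get to the same degree. They are delivered to staff and sites, so they do not appear as a patient's episode of care. If the cost comparison counts only what patients use downstream, it can record a saving in hospital days without subtracting the spending meant to produce it. The result would then be reported as an affordability finding and offered as information for scale-up, where start-up support would be needed again at each new site.

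**Working it through.** The plan states no cost mean, standard deviation, target difference or power for cost, so there is no figure to reproduce. The check compares what is costed with what is supplied, then works out the direction of the omission and an illustrative size.

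1. **Costed against supplied.** The affordability list covers hospital, ED, physician and diagnostic services, public drugs, home care, long-term care and other ambulatory or hospital-based care. The inputs supplied are multi-day training, site visits, a regional PSSP facilitator and continuing ECHO sessions. None is on the list. The top-down step attaches institutional costs to visits or episodes, so it is not a stated route either. The ICES sources named under Objective 2 are not described as holding such costs. The implementation log and ECHO attendance are kept as process data and are not priced.

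2. **Direction.** Let S_N and S_E be mean service costs per patient under NAVIGATE and usual EPI, I the implementation cost beyond the support EPI sites already receive, and N the patients served.
   - Planned difference = S_N − S_E.
   - Inclusive difference = S_N − S_E + I/N.
   - Planned minus inclusive = −I/N, which favours NAVIGATE whenever I > 0.
   - The sign of the conclusion reverses when I/N exceeds the saving S_E − S_N. With the planned log-link model and cost ratio r, that saving is S_E × (1 − r).
   - Neither better matching nor a larger comparison group removes this term.

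3. **Illustrative total (all inputs assumed).** 4 to 9 sites; 0.2 to 0.5 full-time facilitator per site for 1.5 years at 100,000 a year; 8 staff per site trained for 24 hours; 52 ECHO sessions over two years at 1 to 2 hours each; 50 per staff hour.
   - Low: 4×0.2×1.5×100,000 + 4×8×24×50 + 4×8×1×52×50 = 120,000 + 38,400 + 83,200 = 241,600.
   - High: 9×0.5×1.5×100,000 + 9×8×24×50 + 9×8×2×52×50 = 675,000 + 86,400 + 374,400 = 1,135,800.
   - These totals are not net of support that EPI sites already receive. They also omit trainer fees, travel, site visits and ECHO hub time. They could therefore err in either direction.

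4. **Denominator.** Section 2.1 says every patient is offered the NAVIGATE elements, and section 10 says that declining research does not affect receipt of NAVIGATE. The cost is thus shared by all patients served. Section 3.3 expects more than 200 new patients in months 6-12 and more than 400 in months 12-24, so about 600.
   - Over 600: 241,600/600 = 403 and 1,135,800/600 = 1,893.
   - Over the 400 planned participants: 604 and 2,840.
   - Patients already in the programmes, or arriving after month 24, would lower these figures.

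5. **Break-even (comparator mean assumed).** With S_E = 20,000 and r = 0.95, the saving is 1,000 per patient. It is cancelled once I exceeds 1,000 × 600 = 600,000 (400,000 over 400 patients), which lies inside the assumed range. With r = 0.90 the saving is 2,000. Over 600 patients the high case (1,893) falls just short of cancelling it; over 400 patients the high case (2,840) exceeds it.

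**The case against.** The strongest reply is that the scope is disclosed. The subsection says it measures direct patient-level health-service costs, and whether to add programme cost is a choice of costing perspective. Cost is also not the primary system outcome; hospital days are. This stands as far as it goes: the service-cost analysis is valid for what it measures. It does not justify making that figure the sole affordability test, or describing it as the cost associated with NAVIGATE.

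Other points limit the concern:

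- A reader might infer that all of this support falls on the NAVIGATE side. Section 2.1 says PSSP already gives the EPI network in-kind support through annual knowledge exchange and training. Only the increment counts, and the documents do not quantify it.
- PSSP support is meant to taper until it is no longer needed, so start-up and steady-state costs differ. That argues for showing them separately. ECHO is meant to continue.
- Section 2.1 says RAISE needed no new funding for clinical care. That concerns clinical care in the US trial, not training, facilitation or coaching in Ontario.
- A reader might infer that the ICES algorithm could never take such costs, or that the Ministry will decide on this figure alone. The documents say neither. They only summarise the algorithm, and they say that costing adds to policy relevance.
- Part of the Operational Plan text in section 7 was not available for this check, so a costing statement there cannot be excluded. Nothing in the rest of the document points to one.

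**Conclusion.** The concern holds as a bias in the stated affordability test. Followed as written, the NAVIGATE versus usual-EPI cost difference is too favourable to NAVIGATE by the incremental implementation cost per patient. The prediction of lower costs could be reported as confirmed when the inclusive cost is higher. This assumes that some of the support is additional to what EPI sites already get and that the public payer would bear it.

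The size cannot be set from the documents. The ranges of about 400 to 1,900 (600 patients) and 600 to 2,840 (400 participants) rest wholly on assumed staffing, hours and wages. They show only that a modest saving could be offset.

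A reader might go further and infer that NAVIGATE does cost more than usual EPI. The documents do not support that: they contain no cost data, and a large enough service saving would outweigh the omitted amount.

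**What to change.** At minimum, reword hypothesis 2 in section 3.2 and the affordability conclusion in section 4 so that they refer to direct health-service costs, excluding implementation costs. This is a change of text only.

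Preferably, cost the increment as well:

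- Add an hours field to the PSSP facilitator log, which is now described as recording progress, strategies, challenges and milestones, and keep a record of ECHO hub time. Neither can be assumed to exist already.
- Price these together with training days and ECHO staff attendance, counting only what exceeds usual EPI support.
- Spread the total over all patients served by NAVIGATE at the sites, not only consenting participants.
- Show start-up and recurring costs separately.
- Report the NAVIGATE versus usual-EPI difference with and without the increment, and draw the affordability conclusion from the inclusive figure.

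The cost is a small amount of extra time recording by facilitators and the ECHO hub, and a somewhat less favourable cost result for NAVIGATE.

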Matched Controls: Each NAVIGATE subject will be matched to two types of subjects: 1) FEP patients attached to EPI programs who are not participating in the NAVIGATE trial; and 2) FEP patients with no EPI program attachment. Control cases will be matched to NAVIGATE subjects based on OCAN admission date for patients attached to EPI programs and at time of first diagnosis for those patients not attached to EPI programs. Patients with no EPI attachment will be identified using a validated algorithm that identifies all incident cases of psychotic disorders⁶⁹. The diagnostic codes vary by database and included ICD-9, ICD-10, DSM-IV codes. In order to be a FEP case among the non-EPI attached control group, subjects will not have had a non-affective psychotic disorder diagnosis within five years of the matching date. We will use propensity score matching to create the 2 comparison groups of non-NAVIGATE subjects. Propensity score matching mimics the characteristics of a randomized trial using observational data. A propensity score defined as the probability that a person is in the “exposed” category. In this case, the exposure condition is access to the NAVIGATE protocol. The propensity score is developed using logistic regression to model exposure to NAVIGATE as a function of observed covariates to yield a probability of NAVIGATE access for each subject. The propensity score model will include sociodemographic characteristics, clinical factors, and prior service use (defined below). We will match non-NAVIGATE to NAVIGATE subjects based on year of index diagnosis and caliper of the propensity score. Non-NAVIGATE Subjects will be assigned the same admission date as NAVIGATE subjects.

System Outcomes (Hospitalization, ED visits, suicide attempts): Our primary outcome is number of psychiatric hospitalization days in the year following NAVIGATE admission. We will include secondary outcomes, such as ED visits and suicide attempts. Hospitalization-based outcomes will include number of psychiatric hospitalizations and time to first psychiatric hospitalization. We will measure psychiatric emergency department visits with a year of admission as well as ED visits for suicide attempts. Visits to psychiatrists and primary care physicians will also be counted^{70,71}. Visits to primary care physicians will be stratified as mental health related versus non-mental health related based on a previously validated algorithm⁷².

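### The NAVIGATE versus usual-EPI comparison has no covariate for time from first psychosis diagnosis to the start of the outcome year; the planned matching controls it only in part

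*Combined protocol and SAP*

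**What the plan says.** The relevant text is in section 4 of the combined protocol and SAP, under System Level Outcomes + Analytic Plan (Objective 2).

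- **Outcome.** "Our primary outcome is number of psychiatric hospitalization days in the year following NAVIGATE admission".
- **Anchor dates (Matched Controls).** Controls are "matched to NAVIGATE subjects based on OCAN admission date for patients attached to EPI programs and at time of first diagnosis" for those without EPI attachment. The same paragraph adds: "Non-NAVIGATE Subjects will be assigned the same admission date as NAVIGATE subjects".
- **Matching.** "We will match non-NAVIGATE to NAVIGATE subjects based on year of index diagnosis and caliper of the propensity score". No caliper width and no tolerance on the admission date are given.
- **Propensity score.** "The propensity score model will include sociodemographic characteristics, clinical factors, and prior service use (defined below").
- **Covariates.** The list has "sociodemographic characteristics, including age, sex, neighborhood-level income quintile, and rurality of residence". It continues "Clinical covariates will include type of diagnosis (schizophrenia, schizoaffective disorder, etc.), source of index diagnosis (hospitalization, outpatient visit"), then history of alcohol- or substance-related visits. Prior mental health use follows: primary care, psychiatrist and emergency visits, and previous psychiatric hospitalizations. No look-back window or recency is stated.
- **Outcome model (Statistical Analysis).** Hospital days are modelled with adjustment for the same covariates.

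The dates appear to be available. Section 2.1 says of the linked data that "we have confirmed that we can accurately ascertain the initiation date of all EPI patients", and matching on year of index diagnosis already requires a diagnosis date.

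**The concern.** For NAVIGATE patients and EPI-attached controls the outcome year opens at admission, not at diagnosis. If inpatient use is heaviest just after first diagnosis, a patient admitted to the program soon after diagnosis carries more of that early use into the outcome year than one admitted months later, whatever care either receives. Admission speed may be a property of the program, and exposure to NAVIGATE is also assigned by program, so the interval could be linked to both exposure and outcome. An imbalance would bias the primary system-level comparison. It would make NAVIGATE look worse if its sites admit faster, and better if they admit more slowly.

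**Working it through.** **Step 1. Is the interval anywhere in the plan?** Going through the list item by item: age, sex, income quintile, rurality, diagnosis type, source of index diagnosis, substance-related history and prior service counts. None is a time since diagnosis. The five-year look-back for a previous psychotic diagnosis is stated only for controls without EPI attachment, so it does not restrict EPI controls.

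**Step 2. Inputs.** The documents give no inpatient-day profile, no program delays and no power calculation for Objective 2, so there is no plan figure to reproduce. Everything below is assumed and illustrative, with no true treatment effect:

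- Expected inpatient days per month after diagnosis: profile A 4, 2, 1.5, then 1; profile B 8, 3, 2, then 1; profile C 12, 5, 3, 2, then 1.
- Exponential delays from diagnosis to admission, with means of 1 v 2 months or 2 v 3 months.
- Admissions uniform over a calendar year; pairs matched at random on admission week and calendar year of diagnosis.

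**Step 3. Expected days by delay.** With C(t) the cumulative days by month t after diagnosis, a patient admitted at delay d has H(d) = C(d+12) − C(d).

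- A: H(0) = 4 + 2 + 1.5 + 9 = 16.5; H(1) = 2 + 1.5 + 10 = 13.5; H(3) = 12
- B: H(0) = 8 + 3 + 2 + 9 = 22; H(1) = 3 + 2 + 10 = 15; H(3) = 12
- C: H(0) = 12 + 5 + 3 + 2 + 8 = 30; H(1) = 5 + 3 + 2 + 9 = 19; H(3) = 2 + 11 = 13

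**Step 4. Average over delays, before and after the planned date matching.** Ratios are slower group over faster group.

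| Profile | 1 v 2 months, unmatched ratio | 1 v 2 months, matched days (ratio) | 2 v 3 months, unmatched ratio | 2 v 3 months, matched days (ratio) |
|---|---|---|---|---|
| A | 0.94 | 14.3 v 13.7 (0.956) | 0.97 | 13.5 v 13.3 (0.980) |
| B | 0.90 | 17.0 v 15.6 (0.918) | 0.94 | 15.3 v 14.7 (0.962) |
| C | 0.85 | 21.9 v 19.4 (0.886) | 0.91 | 18.7 v 17.6 (0.941) |

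After matching, the spurious difference runs from 1 − 0.956 = 4.4% to 1 − 0.886 = 11.4% for 1 v 2 months (a repeat run gave 0.885, or 11.5%), and from 2.0% to 5.9% for 2 v 3 months. Matching cuts the mean delay gap from about 30 days to about 20 and 15 days respectively.

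**Step 5. Gap within matched pairs.** The mean absolute difference is about 39 days (1 v 2 months) and 55 days (2 v 3 months). About 11% and 20% of pairs differ by more than 90 days; under 0.2% differ by more than 300.

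**Step 6. Cross-check with a different profile.** Take a daily hospital probability of 0.02 plus 0.30 decaying from diagnosis with a half-life of 30, 60 or 90 days. With equal mean delays (30 v 30 days) the matched ratio is 1.00 throughout. With 30 v 60 days, the faster-over-slower ratio after matching is 1.10 to 1.13. With 30 v 120 days it is 1.21 to 1.25. The size therefore depends on the delay gap assumed.

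**The case against.** **The date matching does real work.** A reader might take the unmatched ratios (6% to 15% fewer days for 1 v 2 months, 3% to 9% for 2 v 3) as the bias. The plan does not propose an unmatched design, and the matched figures are smaller. A reader might also infer that matched pairs commonly differ by almost a year, because two patients with the same admission date and diagnosis year could in principle do so. That is a rare tail under these delays. If both were diagnosed in the calendar year of a mid-June admission, the gap cannot exceed about 165 days.

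**The listed covariates are partial proxies.** It is tempting to say they carry nothing about the interval, since an admission one week or six months after a first stay scores the same on hospitalization count, source and diagnosis. But psychiatrist, primary care and emergency visit counts have longer to accrue over six months than over a week. The simulation gives no credit for this, so its figures may be too large. What stands is that counts with no stated recency cannot be relied on to balance the interval.

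**The premises are not in the documents.** Nothing shows early clustering of inpatient days or different admission speeds at NAVIGATE sites. That stands in full, and it rules out claiming that the comparison is biased or in which direction.

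**Time zero is itself unsettled.** Controls are given the NAVIGATE subject's admission date, and section 3.3 (Clinical Assessments) lets patients join the study up to about a year into their EPI program. The interval cannot be fixed until these statements are reconciled. Settling time zero would not by itself balance the interval, however: EPI controls who all keep their own admission dates could still differ in how long after diagnosis they were admitted.

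**Conclusion.** The omission is plain from the text, and the existing controls are partial. The consequence is conditional. If inpatient days concentrate near first diagnosis and admission speed differs between NAVIGATE and other EPI programs, the primary system outcome could show a spurious difference of about 4% to 12% (mean delays 1 v 2 months) or 2% to 6% (2 v 3 months). These figures are after date matching and before any credit for the propensity score. They rest on assumed profiles and exponential delays; a larger delay gap would give more, and equal delays would give none. The direction is unknown, so the bias cannot be assumed conservative. The point is worth acting on because the remedy is small and the comparison serves a primary objective. It is not evidence that the comparison will be wrong.

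**What to change.** In the Covariates paragraph, add the number of days from first recorded psychosis diagnosis, affective or non-affective, to the EPI admission date used as time zero. Both kinds are needed because the inclusion criteria admit bipolar I disorder and major depressive disorder with psychotic features. Include a category for patients with no diagnosis recorded before admission. Enter the variable in the propensity model for the EPI comparison and in the outcome models for that comparison, and report its balance after matching. State first which date is time zero for EPI controls, so that the interval ends there.

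Exact matching within bands of the interval is not needed. On top of admission date, diagnosis year and a caliper, it may lose matches.

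The cost is one more derived variable and one more model term. It should need no new data collection, since diagnosis and EPI initiation dates are already used in the linked ICES data.

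### The cost outcome is all-cause, but matching and adjustment use prior mental-health service use only, so the cost ratio can carry a pre-existing difference in non-psychiatric spending, in either direction

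*Combined protocol and SAP*

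**What the plan says.** The Affordability paragraph (iv, System Outcome – Cost) sets out "to estimate all direct patient-level health care costs incurred by the public third-party payer" in the three comparison groups. Its scope is wide: "We will include costs of hospitalizations (both non-psychiatric and psychiatric"), emergency visits, primary, psychiatric and other physician care, diagnostics, publicly covered drugs, home and long-term care. A residual category takes in "same-day surgery/procedures, cancer and dialysis clinic visits, and other hospital-based care". For analysis, "we will use a generalized linear model with a gamma distribution and log link to model health care costs". That sentence names no covariate, and the paragraph gives no time window for cost.

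The Covariates paragraph that follows lists age, sex, neighbourhood income and rurality. The clinical items are type of diagnosis, "source of index diagnosis (hospitalization, outpatient visit), and history of visits with alcohol- or substance-related diagnoses". It then adds: "We will also measure prior service use for mental disorders, including the number of prior visits for mental health reasons". The remaining prior-use items are psychiatrist visits, emergency visits for mental health or addiction, and psychiatric admissions.

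Under Matched Controls, "The propensity score model will include sociodemographic characteristics, clinical factors, and prior service use (defined below"), so the propensity score draws on the same list. Under System Outcomes, "Visits to primary care physicians will be stratified as mental health related versus non-mental health related", but only as an outcome. Section 3.2, Hypothesis 2, predicts lower costs with NAVIGATE.

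**The concern.** The outcome and the adjustment set do not cover the same ground. The outcome includes physical-health care, while every prior-use term concerns mental health. A propensity score is built to balance the covariates put into it. Two groups can be well matched on psychiatric history and still differ in what they were already costing the payer for other reasons. In a non-randomised comparison that difference enters the cost ratio and cannot be told apart from an effect of NAVIGATE.

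There is also a precision cost. A person's own earlier spending is a natural predictor of later spending, and the plan leaves it out although the planned costing algorithm could produce it.

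At stake are the cost part of Hypothesis 2, system costs under primary objective 2, and affordability, one of the four implementation metrics. Section 2.1 says cost estimation is meant to inform scaling up. The non-mental-health primary care count has the same gap: it is a named outcome without its own prior value among the covariates.

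**Working it through.** **1. Is there a stated figure to reproduce?** No. The plan gives no SD, effect size, correlation or power for cost. It gives only the recruitment target of 400 (Section 3.3). Everything in steps 3 and 4 rests on assumed inputs.

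**2. The lists side by side.**

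| Part of the cost outcome | Matching prior-use covariate |
|---|---|
| Psychiatric admissions | Prior psychiatric admissions |
| Psychiatrist visits | Prior psychiatrist visits |
| Emergency visits, all causes | Mental-health and addiction visits only |
| Primary care, all causes | Mental-health visits only |
| Non-psychiatric admissions | None |
| Other physicians, diagnostics, home and long-term care, day surgery, other hospital care | None |

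No section supplies the missing rows. Age, sex, income, rurality and substance-related visits are at best weak proxies. The remark that model parameters will follow the cost distribution concerns model form, not confounders. The Statistical Analysis paragraph states covariate adjustment only for hospital days.

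**3. Bias if there is no true effect.** Let *s* be the physical share of cost, *q* the ratio of baseline physical cost (NAVIGATE to control), and *p* its persistence into follow-up. Then

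spurious ratio = 1 − *s* × *p* × (1 − *q*).

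With *q* = 0.8 and *p* = 1:
- *s* = 0.1: 1 − 0.1 × 0.2 = 0.98
- *s* = 0.3: 1 − 0.3 × 0.2 = 0.94

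For *s* 0.1 to 0.4, *q* 0.7 to 0.9 and *p* 0.5 to 1.0, the range is 0.995 to 0.88. The sign follows *q*: with *q* = 1.2 and *s* = 0.3 the ratio is 1 + 0.3 × 0.2 = 1.06, against NAVIGATE.

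A simulation (gamma model, log link, robust SEs, 400 per group, 400 replicates, *q* = 0.8) gave:

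| *s* | Ratio, planned covariates | Ratio with prior costs added | False lower-cost findings (nominal 2.5%), planned → added |
|---|---|---|---|
| 0.1 | 0.976 | 1.000 | 4.0% → 2.0% |
| 0.3 | 0.929 | 0.995 | 18.2% → 2.8% |

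The error rates depend heavily on cost variability. The simulated SE of the log ratio was about 0.08. From SE = CV × √(2/400), a CV of 1.5, 2 or 3 gives 0.106, 0.141 or 0.212. The closed form for *s* = 0.3 (ratio 0.94) then gives false-finding rates of 8.4%, 6.4% and 4.8%.

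**4. Precision.** Let ρ be the correlation of prior with follow-up log cost that remains after the listed covariates. On the log-cost scale the variance factor is 1 − ρ²:
- ρ = 0.1: 0.99, equivalent to 400/0.99 = 404 per group
- ρ = 0.3: 0.91, equivalent to 440
- ρ = 0.5: 0.75, equivalent to 533

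For the gamma model (400 v 400, log-normal costs, log-SD 1.2, true ratio 0.80, two-sided 5%), unadjusted power is about 46–50% whatever ρ is. Adding prior cost gains about 1, 7 and 19 points at ρ = 0.1, 0.3 and 0.5. Separate runs of 2,000 replicates gave 1–2, 5–7 and 16–19 points, so these gains are good to a few points only.

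**The case against.** The strongest reply has four parts.

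*The main drivers are already covered.* Psychiatric admissions, psychiatrist visits, mental-health emergency and primary care use, substance-related visits, diagnosis and source of diagnosis are all listed. They suit the stated primary system outcome, psychiatric hospital days. In patients aged 14–35 the physical share of cost may be modest, and listing cancer or dialysis clinics describes the scope of the algorithm, not this cohort's use. This stands, and it limits the severity. It does not remove the mismatch.

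*No imbalance or direction is shown.* A reader might infer that the plan favours NAVIGATE, or that a lower-cost result would be an artefact. The documents support neither: nothing in them indicates which group had the higher physical-health spending.

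*Larger figures are easy to produce but do not describe this problem.* A reader might shift total prior cost by 0.2 SD and, with a correlation of 0.5, obtain a spurious ratio of exp(−0.2 × 1.2 × 0.5) = 0.89. With a prior log-SD of 1.2, that shift means total cost 21% lower (exp(−0.24) = 0.787). Were physical spending the only source, it would have to be 0.213/0.3 = 71% lower at a 30% share; at a share of 20% or less the shift is impossible (0.213/0.2 > 1). Likewise, a power gain at ρ = 0.5 cannot be taken as typical, because ρ is what remains after several psychiatric-use counts. At ρ = 0.1 the gain is negligible.

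*Adding prior cost is not free of difficulty.* Matched Controls anchors EPI patients on programme admission in OCAN and non-EPI controls on first diagnosis. Cost in the year before index could include the diagnostic episode in one group and exclude it in the other. This stands. The listed prior-use counts share the problem, and the fix has to deal with it.

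**Conclusion.** The point holds as a mismatch between outcome and adjustment set. The cost outcome is all-cause, the prior-use terms in both the covariate list and the propensity score are mental-health only, and no prior cost or physical-health measure appears anywhere. The cost ratio can therefore carry a pre-existing difference in non-psychiatric spending, in either direction.

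The size cannot be derived from the documents. Under the assumptions shown, the bias is small when physical care is about a tenth of cost and becomes material at about 30% with a persistent imbalance. The precision loss ranges from negligible to worthwhile, depending on an unstated correlation. Since psychiatric visit counts already capture part of prior psychiatric cost, the core gap is prior non-mental-health use. I rate it minor to moderate: cost belongs to a primary objective and to Hypothesis 2, but it is not the stated primary system outcome.

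**What to change.** In the Covariates paragraph:

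- Add non-psychiatric cost in the prior year, or total prior-year cost split into psychiatric and non-psychiatric parts, from the same ICES costing algorithm.
- Add prior non-mental-health primary care visits.
- Put both in the propensity score, and state that the gamma/log-link cost model adjusts for them along with the listed covariates.
- Report their standardised differences after matching for each of the two comparisons.
- Define the look-back window so that it ends at a comparable point in all groups, for example before first psychosis diagnosis, and state the follow-up window for cost.

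If non-mental-health primary care visits are to be modelled, name a model for that count and adjust for its prior value. The Statistical Analysis paragraph names only logistic and Cox models for secondary outcomes.

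The cost is plan wording, one more run of an algorithm already in use on records already to be linked, a slightly larger propensity model, and the work of setting the window. No new data collection or patient contact is needed.
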